**Trial Status**

This trial was registered prospectively in January, 2020 at ClinicalTrials.gov (NCT04287413). Recruitment of primary care sites (clusters) was completed in June 2023 (after being delayed due to the COVID-19 Pandemic). Cluster randomization was performed in July 2023. Patient participant recruitment was initiated in October, 2023 and completed in November, 2024. Data collection is ongoing as of the submission of this protocol with data collection planned for completion by December 19, 2025. Data analysis will be carried out in accordance with this pre-specified analysis plan and will commence following the completion of data collection. No interim analyses have been conducted. Results are expected to be published in 2026.

## Introduction

Low back pain (LBP) is the world's largest contributor to years lived with disability, costs the Canadian healthcare system between \$6 and \$12 billion annually, and is a leading contributor to lost work productivity. The burden of LBP on the healthcare system is evidenced by frequent healthcare use, including unnecessary specialist consultations, diagnostic procedures, opioid prescriptions, and emergency department visits.

LBP is the fifth most common reason for physician visits with primary care physicians being the most frequent first point of contact within the healthcare system for people with LBP. A Lancet series on LBP highlighted international expert consensus on the need to evaluate new primary care models that better support physicians, who receive limited training in the management of musculoskeletal (MSK) conditions and report low confidence addressing LBP. One of these models involves integrating physiotherapists (PTs) within primary care teams at the first point of contact, which has the potential to provide patients with a more focused LBP consultation, assist with evidence-based treatment delivery, reduce low-value care (such as inappropriate imaging, specialist physician referrals, and opioid prescriptions), and reduce primary care physician visits. If integrating PTs can reduce primary care physician visits, it could contribute to increasing the capacity of primary care teams to help address the growing challenge of providing universal access to primary care in the context of more complex patient encounters, increasing prevalence of multiple chronic conditions, and an aging population.

Evidence suggests PTs can provide collaborative care and implement recommendations from LBP primary care guidelines, including: screening for serious pathology, the need for diagnostics and identifying risk factors for poor recovery; providing reassurance, encouragement for early return to work, and exercise and physical activity recommendations; and delivering targeted, psychologically informed interventions for those at risk of prolonged recovery. Evidence from outside of Canada suggests that early guideline adherent PT care for LBP improves function and disability while reducing diagnostic imaging, opioid prescriptions, and physician specialist referrals, and reduces per-person healthcare costs.

Evidence from observational research suggests that involving PTs in providing first-point-of-contact care (i.e., PT-led care) for those with work-related injuries in the US military resulted in workers being more satisfied with their care, receiving faster access to treatment, having fewer sickness absences, and using PTs and specialist physicians more appropriately. Observational studies from the UK National Health Service on first-contact PT models of care indicate similar health outcomes, high levels of patient and physician satisfaction, shorter physician wait times, fewer work absences and diagnostic images, lower prescription medication use, and reduced costs.

The absence of high-quality randomized trials of PT-led primary care models leaves important unanswered questions about the process and impact of integrating PTs within primary care teams for people with LBP. Specifically, there is a need for higher quality evidence on the impact of PT-led primary care on patient-oriented outcomes (e.g., function, pain, quality of life), health system outcomes (e.g., healthcare access, physician workload, emergency department visits, specialist physician referrals, medication use, diagnostic imaging), and societal outcomes (e.g., missed work, cost-effectiveness). Also, it is unclear how PTs will navigate primary care challenges, such as providing care for people presenting with multiple health concerns or addressing requests for medications, diagnostic imaging, or notes for work absences. This cluster randomized trial and embedded process evaluation will address these gaps by assessing the impact and implementation of a PT-led primary care model for LBP. The

results will inform primary care transformations across multiple health systems and potentially improve outcomes for patients with LBP.

The purpose of publishing this protocol and analysis plan is to transparently report our design and methods, and to transparently communicate our analytic plan in advance of carrying out our planned analysis to reduce the risk of analytic or reporting bias.

### **Research Questions:**

- 1) Is a PT-led primary care model for LBP effective at improving disability (primary outcome), pain intensity, quality of life, global rating of change, patient satisfaction, and adverse events compared to usual physician-led primary care, when evaluated over a one-year period?
- 2) What is the impact of a PT-led primary care model for LBP on the health system and society (healthcare access, primary care physician workload, healthcare utilization, missed work, cost-effectiveness), evaluated over a one-year period?

### **Methods**

#### **Trial Design:**

The trial is a parallel arm cluster randomized controlled trial at 20 primary care sites randomized 1:1 to a PT-led or usual physician-led primary care model for LBP. Randomization of practices, rather than patient participants, allows evaluation of a model where PTs are able to fully integrate within the primary care team and reduces potential contamination between study arms. This protocol and analysis plan includes all of the items included in the Standard Protocol Items: Recommendations for Interventional Trial (SPIRIT) reporting guidelines. See Table 1 for a summary of the schedule of enrolment, interventions and assessments.

**Table 1.** Schedule of enrolment, interventions, and assessments.

	STUDY PERIOD							
	Enrolment of clusters	Allocation of clusters	Enrolment of patient participants	Post-allocation				Close-out
TIMEPOINT	Pre-intervention	Pre-intervention	0 (baseline)	6 wk	12 wk	6 mo.	9 mo.	12 mo.
ENROLMENT OF PRIMARY CARE SITES:								
Eligibility screen	X							
Informed consent	X							
Allocation to study group		X						
ENROLMENT OF PATIENT PARTICIPANTS:								
Eligibility screen			X					
Informed consent			X					
INTERVENTIONS:								
PT-led primary care				↔				↔

Usual care								
ASSESSMENTS:								
Participant characteristics and demographic information			X					
Participant health outcomes (RMDQ, pain intensity, EQ-5D-5L, PSEQ, PCS, TSK-11, PHQ-2)			X	X	X	X	X	X
Participant health and experience outcomes (Satisfaction, GROC, adverse events)				X	X	X	X	X
Health system and societal outcomes (provider encounters, EHR utilization, healthcare utilization, missed occupational activities, assistance required)				X	X	X	X	X
Implementation measures (timely access, PT as first point of contact, access to PT, LBP management)			X	X	X	X	X	X
Implementation measures (patient adherence)				X				
QUALITATIVE INVERVIEWS:								
Patient participants					X			
Primary care providers and leads, medical office assistants*							X	X

\* These interviews started 9 months after study launch.

The trial incorporates a multi-methods process evaluation informed by United Kingdom Medical Research Council (MRC) guidance for developing and evaluating complex interventions, the Consolidated Framework for Implementation Research (CFIR), and findings from the process evaluation from our pilot trial. Process evaluations assess how interventions were implemented and under what conditions. They are important to help interpret trial results (e.g., explaining why an intervention fails or has unexpected consequences, or why it works and how it can be refined). Process evaluations can be particularly valuable for informing future implementation and sustainability of complex healthcare interventions. Our process evaluation is informed by and intended to refine our program theory for the PT-led primary care model program for LBP (**Figure 1**). The program theory

describes how the PT-led primary care model for low back pain is intended to lead to improvements in trial outcomes.

### **Allocation of Participating Primary Care Teams to Trial Groups:**

Restricted randomization is recommended for cluster randomized trials to ensure the arms are balanced at baseline. We used covariate-constrained randomization with 1:1 ratio to the intervention and comparison arms to retain the merits of random allocation while ensuring baseline balance across the arms. We stratified by location (Southeastern Ontario or Interior British Columbia) and included the following covariates: number of active patients and rural vs. urban setting. Our maximum tolerable difference in the rurality indicator was 1 and the strata balancing criteria for number of active patients was set to 10%. An independent statistician implemented the procedure using a SAS macro. Concealment was maintained by ensuring each practice had an anonymized code and performing randomization after all sites were recruited.

### **Methods for Protecting Against Sources of Bias:**

Due to the trial design and interventions being compared, the PTs, patient participants, other members of the primary care team, and research assistants have not been blinded. While limitations due to the inability to blind are unavoidable, we have taken additional steps to minimize the risk of bias suggested for cluster trials. A common challenge in cluster trials is identification and recruitment bias when patient recruitment must take place after cluster allocation. To minimize the risks of these biases, we invited consecutive patients to participate, provided the same information about the trial to both groups prior to participants consenting (not revealing the cluster allocation until after consent and baseline data collection), employed research assistants unfamiliar with the patients to recruit and consent participants, and rigorously applied inclusion/exclusion criteria at all sites.

### **Inclusion/Exclusion Criteria:**

For primary care sites, inclusion criteria were:  $\geq 2$  family physicians and/or nurse practitioners and  $\geq 1,500$  active patients. Exclusion criteria were: already having a PT on the team or no space available for a PT to practice. Patient participants were screened prior to consent by a trained research assistant at both intervention and comparison sites. Inclusion criteria for patients participants were: adults ( $\geq 19$  years of age) with LBP of any duration, who were able to read, write and speak English. Exclusion criteria were: known cancer that could possibly contribute to LBP or inability to complete the scheduled follow-ups over one-year.

### **Recruitment:**

We recruited 20 sites (14 in Ontario and 6 in British Columbia, Canada). Site recruitment focused primarily on the engagement of contacted sites to reduce the risk of site withdrawl. For patient participant recruitment, staff at each primary care site screened patients for their willingness to participate when they called to book an appointment. If patients booked online, their reason for visit was screened by the clinic staff and staff reached out to potential participants for their willingness to be contacted by a research assistant. Trained research assistants screened potential participants using inclusion/exclusion criteria and enrolled consenting patients. Patients who raised LBP with any provider during a clinical encounter were also identified as potential participants. In these cases, they were directed to the administrative team, who then connected them with a research assistant for screening and enrollment. Balance in recruitment across arms and across clusters was monitored throughout the study and strategies were implemented to maintain consistent implementation of recruitment processes across sites.

### **Sample Size and Power Calculations:**

We used the methodology of Teerenstra et al. to calculate the required number of clusters based on an ANCOVA analysis for the primary outcome (Roland-Morris Disability Questionnaire [RMDQ]) at 12 months adjusting for baseline. Our target sample was 20 clusters (10 per arm) allowing for 1560 patient participants (78 per practice before attrition). Conservatively accounting for attrition of two clusters (resulting in 18 clusters) and 20% of patients (resulting in 63 patients/cluster), this target would achieve 90% power to detect a minimally important mean difference of 2.5 points (Cohen's  $d=0.4$ ) using a two-sided  $\alpha=0.05$  and assuming a standard deviation (SD) of 5.7 points based on pilot study data, a conservative intracluster correlation coefficient of 0.1, a cluster autocorrelation coefficient (correlation between cluster means at baseline and follow-up) of 0.5, and an individual autocorrelation coefficient (correlation between participant scores at baseline and follow-up) of 0.6 informed by our pilot study. An average rate of 1.5 patient participants per site each week over one year would achieve the recruitment target of 1560 participants, which we anticipated based on our pilot study where we recruited and retained four sites and achieved a recruitment rate of >1.7 participants/site/week. Recruitment of 400 patient participants across 18 clusters (22 participants/cluster) would achieve 80% power.

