### **Clinical Partner Sites:**

This study is being coordinated from a primary Research Coordinating Centre at Queen's University with 20 participating primary care sites (clusters) between Southeastern Ontario (14) and Interior British Columbia (6), Canada. Sites include representation from urban and rural settings in both regions to facilitate generalizability.

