#### **Patient health and experience outcomes**

For our patient health outcomes, we will use linear mixed models to estimate individual patient participant outcomes adjusting for clustering by primary care centre. Our primary outcome (RMDQ) with repeated measures at baseline and the 6-week, 3-, 6-, 9-, and 12-month follow-up time points will be analyzed using linear mixed regression (using *PROC MIXED* in SAS), estimated using restricted

maximum likelihood (REML) estimation and a Kenward-Rogers degrees of freedom correction to account for a small number of clusters. The model will include fixed effects for time, intervention group by time interaction, (omitting the group main effect to ensure baseline differences are constrained to zero), factors used in the covariate-constrained allocation procedure (rurality of the cluster, number of active patients) and other pre-specified covariates associated with LBP-related disability (patient participant age, sex, income, highest level of education achieved, duration of current episode of LBP, Functional Comorbidity Index score). The correlation in repeated measures on the same participant will be modeled using a suitable covariance structure, identified using information criteria (AIC/BIC). To account for clustering within practices, site will be modeled as a random effect. The intervention effect will be obtained as the adjusted least square mean difference between arms at 12 months, with 95% confidence intervals. Secondary comparisons will be obtained using least square mean differences at intermediate time points.

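### The 90% power stated for 18 clusters of 63 patients matches normal critical values (89.3%); with cluster-limited degrees of freedom the same inputs give about 85%

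*Combined protocol and SAP*

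**What the plan says.** The section on sample size and power in the combined protocol and SAP uses a published ANCOVA method for cluster trials, applied to the 12-month RMDQ with baseline adjustment. The scenario is described as "Conservatively accounting for attrition of two clusters (resulting in 18 clusters) and 20% of patients (resulting in 63 patients/cluster", and the claim is that "this target would achieve 90% power to detect a minimally important mean difference of 2.5 points". The inputs are a two-sided 5% level, an SD of 5.7, "a conservative intracluster correlation coefficient of 0.1", "a cluster autocorrelation coefficient (correlation between cluster means at baseline and follow-up) of 0.5", and an individual autocorrelation of 0.6. A second figure is 80% power with 400 patients in 18 clusters (22 each). Neither figure comes with a reference distribution or df.

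The analysis section on patient health and experience outcomes fits the primary model by REML with "a Kenward-Rogers degrees of freedom correction" "to account for a small number of clusters". On clustering it says: "To account for clustering within practices, site will be modeled as a random effect". The within-participant covariance structure is to be chosen by AIC/BIC. The section on clinical partner sites describes the study as coordinated "with 20 participating primary care sites (clusters".

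**The concern.** With 18 clusters, the between-cluster variance that dominates the standard error is estimated from few units. The plan accepts this for the analysis, where it commits the primary test to a small-sample correction. The printed power equals what a test without that correction would have. If the planned test is cluster-limited, a true 2.5-point difference would be missed about 13-15% of the time in this scenario, not 10%, and the difference detectable with 90% power would be larger than 2.5 points. This matters mainly for interpreting a null result. The scenario is also the one the plan presents as conservative, so a reader would assume that the small-cluster penalty is already included.

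**Working it through.** **Inputs**, all from the section on sample size and power: K = 18 clusters (taken as 9 per arm), n = 63 per cluster, SD = 5.7, ICC = 0.1, cluster autocorrelation (CAC) = 0.5, individual autocorrelation (IAC) = 0.6, difference 2.5, two-sided 0.05.

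**Step 1. Standard error.**
- Design effect: DE = 1 + (n - 1) x ICC = 1 + 62 x 0.1 = 7.2.
- Correlation of cluster means between baseline and follow-up: r = [n x ICC x CAC + (1 - ICC) x IAC] / DE = (3.15 + 0.54) / 7.2 = 0.5125, so 1 - r² = 0.7373.
- Var = 4 x SD² x DE x (1 - r²) / (n x K) = 4 x 32.49 x 7.2 x 0.7373 / 1134 = 0.608, so SE = 0.780.
- Effect / SE = 2.5 / 0.780 = 3.205.

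**Step 2. Reproduce the printed figure.** With normal critical values, power = Φ(3.205 - 1.960) = 89.3%. This rounds to the printed 90% within tolerance. With a t reference, 100 df give 88.8%, and about 166 df are needed for 89.0%.

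**Step 3. Same noncentrality (3.205), cluster-limited df.** The plan gives no df, so these are assumptions:

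| Reference | Power, 18 x 63 |
|---|---|
| t, 14 df (clusters minus 2, less two cluster-level covariates) | 84.6% |
| t, 16 df (clusters minus 2) | 85.3% |
| t, 25.3 df (see below) | 86.9% |
| Normal | 89.3% |

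The 25.3 df come from a model with two time points, a constrained baseline, and both site and site-by-time effects. The sum and difference of the two cluster means have variances proportional to 1 + r and 1 - r, each estimated on K - 2 df. The Satterthwaite df are then 2(K - 2) / (1 + r²) = 32 / 1.2627 = 25.3.

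**Step 4. Simulation of that two-time-point model** (400,000 replicates, estimated weights, equal cluster sizes). A Kenward-Roger-type adjustment gave 85.4% power at 5.2% type I error. Normal critical values gave 89.1% power, but at 7.4% type I error. So 86.9% is an upper value, and about 85% is the better single figure. The simulation uses two of the six time points.

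**Step 5. Difference detectable with 90% power at 18 x 63:** 2.53 points (normal), 2.63 (25 df), 2.70 (16 df).

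**Step 6. All 20 clusters at 63 each:** SE = 0.740 and effect / SE = 3.378. Power is 89.1% at 18 df, 90.1% at 25 df and 92.2% with normal values.

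**Step 7. The second printed figure, 80% at 18 x 22.** DE = 3.1, r = 1.64 / 3.1 = 0.529, Var = 4 x 32.49 x 3.1 x 0.7201 / 396 = 0.733, and effect / SE = 2.921. Power is 83.2% (normal), 80.2% (25 df) and 78.3% (16 df). If 20% attrition is applied to the 22 (22 x 0.8 = 17.6 per cluster), normal values give 80.8%. The printed 80% therefore fits either small-sample df without attrition or normal values with attrition, and does not show which reference was used.

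**The case against.** The strongest reply has four parts.

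- **The 90% reproduces from the plan's inputs.** This stands. A reader might infer a slip of arithmetic, but 89.3% is within tolerance of 90%. The issue is the choice of reference distribution, and even normal values are inferred, because the plan names none.
- **The alternative df are not in the documents.** This also stands. Read literally, with only a site random intercept plus participant covariance, the two-time-point model has Satterthwaite df of about 1,130, and the correction would cost almost nothing. But a site effect that is constant over time contradicts the plan's own CAC of 0.5, under which site effects change between baseline and follow-up. That reading therefore does not support 90% under the stated assumptions. Nor can the actual df be fixed while the covariance structure is open.
- **The upper end of the range is soft.** This stands too: 87% needs about 25 df, and the simulation reaches only 85.4%.
- **The consequence is small.** This largely stands. Eighteen clusters is an allowance, 20 sites are participating, the ICC is called conservative, and the analysis adjusts for prognostic covariates that the power figure does not credit. The documents size neither of the last two. A reader might infer that the trial is underpowered; the documents do not support that, since 20 x 63 gives about 89-90%.

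**Conclusion.** The point holds as a reporting matter. The stated 90% for 18 x 63 is reached only with normal or very large df critical values, while the plan commits the primary test to a correction for few clusters. Under cluster-limited df the power is about 85%, with a range of 84-87% for 14 to 25 df. That is roughly 3 to 5 percentage points below the printed figure.

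This rests on the plan's own variance inputs, equal clusters with 9 per arm, and assumed df chosen to agree with the CAC of 0.5. The range is before any gain from covariate adjustment or an ICC below 0.1. To restore 90% at 18 x 63, the variance would have to be 14% lower (16 df) or 10% lower (25 df), or the ICC would have to be about 0.084 or 0.089 respectively. The 20-cluster figure assumes 63 analysed patients per cluster; the documents do not report the numbers achieved.

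**What to change.** In the section on sample size and power:

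1. State the reference distribution and df behind both the 90% and the 80% figures, and whether the 22 per cluster is before or after attrition.
2. Restate the power for 18 x 63 as about 85% (84-87% for 14 to 25 df), before any gain from covariate adjustment or an ICC below 0.1.
3. Add that 20 x 63 gives about 89-90% (18 to 25 df).
4. If the calculation already used small-sample df or other inputs, print those instead of items 2 and 3.

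The 80% can stand as approximate once its basis is given. The cost is a few lines of text and one slightly less favourable figure. Patient recruitment is complete, and no change to sample size, estimation or testing is needed. According to the section on trial status, analysis starts only after data collection ends, so the wording can be corrected before results are known.
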